### **Local tolerability Abnormalities**

The following summary tables will be provided:

- A summary of the number and percentage of participants reporting a local tolerability reaction, by gender, SOC and PT,

The following listing will be provided:

- A listing of all local tolerability reactions that occurred during the study.

#### **5.8.4     *Laboratory Data***

All laboratory data will be presented in the units of International System of Units (SI).

Describe the summaries that are to be provided. These may include the following summaries:

- A summary of the actual and change from baseline in each laboratory parameter by gender group and timepoint,
- A summary of the number and percentage of participants experiencing treatment-emergent clinically significant laboratory abnormalities, by gender group and laboratory parameter,
- A shift from baseline to worst post-dose (i.e. highest grade) in CTCAE Grade of laboratory results.

For shift tables, the denominator should be the number of participants with both a baseline and a post-baseline assessment at a given timepoint.

In addition, the following listings are to be provided:

- A listing of all laboratory data. Out-of-reference-range values will be flagged as high (H) or low (L),
- A listing of CTCAE grade 3 and higher values. All data for a laboratory parameter will be displayed for a participant who has any post-baseline value with CTCAE grade greater than or equal to 3 for the parameter.

#### **5.8.5 *Vital Signs***

Describe the summaries that are to be provided. These include:

- A summary of the actual and change from baseline in each vital sign parameter by gender group and timepoint,

#### **5.8.6 *Electrocardiogram (ECG)***

Not applicable.

#### **5.8.7 *Physical Examination***

Physical examinations, including body weight (kg) and body height (cm), will be conducted at Baseline (Visit 2), at Visit 3 and at Visit 4 if applicable.

The following summary and listings will be provided:

- A shift from baseline (normal vs abnormal) to each post-baseline visit
- A change from baseline to each post-baseline visit
- A listing of physical examination data,
- A listing with any participants with at least one physical examination abnormality.

#### **5.8.8 *Other (if applicable)***

Participants are to be discontinued from the study if they become pregnant. Pregnancy data will be shown in a data listing if applicable. No special analysis will be performed on the pregnancy.

#### **5.9 *Efficacy and Safety Evaluations (Extension Phase)***

An additional analysis on efficacy and safety endpoints will be performed considering the extension phase duration, a period of an additional 6 months, lasting until the End of Extension Phase Visit at Month 12.

As this is an extension phase following the main study phase, the efficacy and safety endpoints in the extension phase will be summarised descriptively. No formal statistical hypotheses testing will be performed.

Statistical analyses will include the following:

- For the continuous endpoints, the descriptive summary statistics (number of participants (n), mean, SD, median, minimum, maximum) will be calculated
- For the categorical endpoints, the summary statistics of number and percentage of participants and the exact two-sided 90% confidence interval (CI) will be calculated.

### 5.9.1 *Efficacy Endpoint for Extension Phase*

The extension phase efficacy endpoints are the following:

**Table 2 Efficacy Endpoints and Evaluations of extension phase**

Measure	Timepoint	Variable	Endpoint
Basal LH and FSH serum levels	Baseline, Month 9 and Month 12 (EOEP)	LH and FSH concentration	Change in basal serum LH and FSH levels at Month 9 and Month 12 compared to baseline
Peak LH after GnRH stimulation test	Baseline and Month 12 (EOEP)	Peak LH levels after GnRH stimulation (30, 60 and 90 minutes)	Change in peak LH levels after GnRH stimulation test at Month 12 compared to baseline; Proportion of children with LH suppression defined as stimulated peak LH $\leq 3$ IU/L after GnRH stimulation at Month 12.
Peak FSH levels after GnRH stimulation test	Baseline and Month 12 (EOEP)	Peak FSH levels after GnRH stimulation (30, 60 and 90 minutes)	Change in peak FSH levels after GnRH stimulation test at Month 12 compared to baseline.
E2 and testosterone serum concentrations	Baseline, Month 9 and Month 12 (EOEP)	Sex steroids levels	Proportion of children with sex steroids suppressed within prepubertal ranges (E2 $\leq 20$ pg/mL in girls and testosterone $\leq 0.3$ ng/mL in boys); Change in sex steroids levels compared to baseline
Pubertal stage (Tanner Method)	Baseline, Month 12 (EOEP)	Pubertal stage	Change in pubertal stage (genital stage in boys, breast stage in girls and pubic hair stage in both sexes) compared to baseline; Proportion of children with stabilised pubertal stage compared to baseline

Auxological parameters (height, growth velocity, weight, BMI)	Baseline, Month 9 and Month 12 (EOEP)	-	Change in auxological parameters compared to baseline
BA	Baseline, Month 12 (EOEP)	-	Change in BA, difference between BA and CA compared to baseline
Uterine length or testis volume	Baseline, Month 12 (EOEP)	Gonad development	Change in uterine length in girls and testicular volume in boys compared to baseline

BA = Bone age; BMI = Body mass index; CA = Chronological age; EOEP = End of Extension Phase; FSH = Follicle stimulating hormone; GnRH = Gonadotropin-releasing hormone; LH = Luteinising hormone; E2 = Oestradiol.

Unless otherwise specified, all analysis of extension phase efficacy endpoints will be the same as main study phase.

For extension phase efficacy endpoints related to a change at Month 9 and Month 12 compared to baseline, the descriptive summary statistics (n, mean, SD, median, minimum, maximum) will be calculated on the ITT and PP. Exact two-sided 90% CIs will also be constructed for all extension phase efficacy endpoints expressed as percentages.

### 5.9.2 Safety Endpoint for Extension Phase

The extension phase safety endpoints are the following;

- Incidence of treatment-emergent adverse events (TEAEs) throughout the study, including local tolerability
- Change in clinical safety laboratory (blood biochemistry, haematology and urinalysis) parameters at Months 9 and 12
- Change in physical examination and vital signs (blood pressure and heart rate) measurements at each visit

Unless otherwise specified, all the analysis of extension phase safety endpoints including AE, laboratory, physical examination and vital signs will be the same as main study phase.

### 5.10 Pharmacokinetics

Pharmacokinetics analysis is only for main study phase.

The individual plasma triptorelin concentration are measured in all subjects receiving study drug on Day 1 (to be taken predose and at 4 hours post-injection); at Month 3 visit (to be taken predose); and Month 6 EOS/early withdrawal visit. Individual listings and descriptive summary statistics will be presented for triptorelin plasma concentrations.

Descriptive statistics (n, mean, SD, SEM, %CV, 95% lower CI, 95% upper CI, median, minimum and maximum, geometric mean, geometric SD, geometric CV%, 95% Lower Geomean CI, 95% upper Geomean CI) will be summarized by each scheduled visit, and by timepoint where applicable. To compute descriptive statistics, all BLQ values must be replaced by missing in the data set. BLQ values substituted by missing are excluded in the calculation of descriptive statistics.

Triptorelin concentrations will be displayed with the same precision as the BLQ values. For the descriptive statistics, calculations derived from concentrations (mean, min, max, median, SD etc.) will follow the same rule as Min and Max, but coefficient of variation (CV%) will be displayed with one decimal digit only.

The descriptive statistics should be displayed by visit/time point, only if at least 2/3 (2 out of every 3 values) of the data are available and above the limit of quantification. Otherwise, only minimum and maximum are reported. Individual and mean plasma concentration time profiles, as well as spaghetti plots, on the PK Set will be generated.

If required and warranted by the data, an attempt to build a model to characterize the PK in the population will be made.

This will be described in a separate analysis plan and the outcomes summarised in a standalone report.

#### **5.11 Anti-drug Antibodies (if applicable)**

Not applicable.

#### **5.12 Pharmacodynamics (if applicable)**

Not applicable.

### **6 DATA HANDLING**

#### **6.1 Visit window**

All data will be organized and analysed according to the scheduled visits outlined in the protocol. As defined by the protocol, visit 1 (Screening visit) has to be performed within Day -28 to Day -1 prior to first treatment. Visit 2 (Baseline visit) will be the day of first treatment. Visit 3 will correspond to Day 88 to Day 94 and participants who complete the study will perform final procedures and assessments at the final visit (Month 6).

Participants who withdraw from the study before the completion of the evaluation period will be invited to attend an Early Withdrawal visit to perform early discontinuation procedures and assessments.

For participants who do not have a final visit within 3 months (i.e. up to Day 182±3 days as in Protocol Table 1) after their last triptorelin dose, efficacy evaluations should not be performed. Data from any efficacy evaluations performed after this time will not be collected on the eCRF.

#### **6.2 Unscheduled Visits, Retest, Withdrawal Visit,**

All listings will include retests and unscheduled visits, while for the description by visit in the tables, only the scheduled visits according to the protocol will be described.

Unscheduled visit and retest measurements will be used to provide a measurement for a baseline data or endpoint value (e.g. worst value), if appropriate according to their definition. These measurements will also be used to determine abnormal laboratory, vital signs values or ECG.

If a value requires a retest (for laboratory values and vital signs) the closest non-missing reliable value to the scheduled visit will be used in the summary tables.

Participants who have withdrawn early from the study have their last assessment entered as visit 90 in the electronic Case Report Form (eCRF).

### **7 DERIVED DATA (IF APPLICABLE)**

When applicable, below derivation rules should be followed:

- Change from baseline**

Change from baseline at a given visit will be calculated as a difference from baseline.

- Age**

Age (years) will be calculated as follows and truncated to the largest integer that is less than or equal to the calculated result:

Age = (informed consent date of main study phase - birth date + 1)/365.25.

- **Chronological Age**

Chronological Age (years) will be calculated as follows and truncated to the largest integer that is less than or equal to the calculated result:

Chronological Age = (Visit Date - birth date + 1)/365.25.

- **BMI**

BMI (kg/m^2) will be derived as Weight (kg)/[Height(cm)/100]\*\*2 measured at each visit and rounded to the nearest decimal.

- **Bone Age**

For bone age recorded as 9+ or 10-, the original result will be listed in listing and update 9+ to 9.25 and 10- to 9.75 in the summary analysis.

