7.2 Secondary Efficacy Endpoints and Evaluations

Secondary efficacy endpoints and evaluations are summarised in [Table 5](#). For this study, baseline values correspond to those obtained with measurements performed at the Screening visit.

Table 5 Secondary Efficacy Endpoints and Evaluations

Measure	Timepoint	Variable	Endpoint
Basal LH and FSH serum levels	Baseline, Month 3 and Month 6 (EOS)	LH and FSH concentration	Change in basal serum LH and FSH levels at Month 3 and Month 6 compared to baseline
Peak LH after GnRH stimulation test	Baseline, Month 3 and Month 6 (EOS)	Peak LH levels after GnRH stimulation (30, 60 and 90 minutes)	Change in peak LH levels after GnRH stimulation test at Month 3 and Month 6 compared to baseline; Proportion of children with LH suppression defined as stimulated peak LH ≤ 3 IU/L after GnRH stimulation at Month 6.
Peak FSH levels after GnRH stimulation test	Baseline Month 3 and Month 6 (EOS)	Peak FSH levels after GnRH stimulation (30, 60 and 90 minutes)	Change in peak FSH levels after GnRH stimulation test at Month 3 and Month 6 compared to baseline.
E ₂ and testosterone serum concentrations	Baseline, Month 3 and Month 6 (EOS)	Sex steroids levels	Proportion of children with sex steroids suppressed within prepubertal ranges (E ₂ ≤ 20 pg/mL in girls and testosterone ≤ 0.3 ng/mL in boys); Change in sex steroids levels compared to baseline
Pubertal stage (Tanner Method)	Baseline, Month 6 (EOS)	Pubertal stage	Change in pubertal stage (genital stage in boys, breast stage in girls and pubic hair stage in both sexes) compared to baseline; Proportion of children with stabilised pubertal stage compared to baseline
Auxological parameters (height, growth velocity, weight, BMI)	Baseline, Month 3 and Month 6 (EOS)	-	Change in auxological parameters compared to baseline

Measure	Timepoint	Variable	Endpoint
BA	Baseline, Month 6 (EOS)	-	Change in BA, difference between BA and CA compared to baseline
Uterine length or testis volume	Baseline, Month 6 (EOS)	Gonad development	Change in uterine length in girls and testicular volume in boys compared to baseline

BA = Bone age; BMI = Body mass index; CA = Chronological age; EOS = End of Study; FSH = Follicle-stimulating hormone; GnRH = Gonadotropin-releasing hormone; LH = Luteinising hormone; E₂ = Oestradiol.

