7.4 Methods and Timing of Assessing, Recording and Analysing Efficacy Data

Laboratory tests for efficacy will be performed centrally. The laboratory methods for assessing efficacy data are listed in [Section 5.3](#). The timing of efficacy assessments is summarised in [Table 1](#). Procedures for recording efficacy data are discussed in [Section 15.1](#) and methods of analyses are discussed in [Section 11.4.4](#).

7.4.1 *Change in Luteinising Hormone and Follicle-stimulating Hormone Serum Concentrations*

These parameters will be analysed centrally, as indicated in [Section 5.3](#). The preparation and storage of samples are described separately in the Laboratory Manual.

7.4.2 *Gonadotropin-releasing Hormone Stimulation Test*

Gonadorelin, a synthetic GnRH (manufacturer to be defined), will be used for gonadotrophin stimulation. Gonadorelin used for GnRH stimulation test will be prepared by the investigator sites.

Blood samples will be collected prior to gonadorelin injection (timepoint T0) and at 30 minutes (T30), 60 minutes (T60) and 90 minutes (T90) (± 5 minutes at each timepoint) after a single i.v. injection of gonadorelin with 2.5 μ g/kg (maximum 100 μ g).

A suppressed LH response to GnRH stimulation test is defined as peak LH ≤ 3 IU/L among the four timepoints (T0, T30, T60 and T90).

The FSH response to GnRH stimulation will be the peak FSH level among the four timepoints (T0, T30, T60 and T90).

7.4.3 *Change in Sex Steroids (Oestradiol and Testosterone Serum Concentrations)*

These parameters will be analysed centrally, as indicated in [Section 5.3](#). The preparation and storage of samples are described separately in the Laboratory Manual.

7.4.4 *Change in Pubertal Stage Using the Tanner Method*

See Pubertal Stages According to the Tanner Method ([Appendix 1](#)) for details.

7.4.5 *Auxological Parameters, Bone Age and Chronological Age Measurements and Gonad Development*

Bone age determination (in years and months) will be performed by X-rays of the hand and wrist and estimated by the Greulich and Pyle method [[Greulich 1959](#)].

Gonad development (uterine length or testis volume) will be determined by type B ultrasound.

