### **5.4 Demography and Other baseline characteristics**

All demographic and baseline characteristics summaries and listings will be provided for ITT, mITT, PPS and safety population.

Following summaries will be provided on:

- Demographic variables (age, ethnicity, sex)
- Other baseline characteristics (height, weight, BMI, pubertal stage, growth velocity, bone age, chronological age, the difference between bone age and chronological age),

- Baseline Disease characteristics (Time from initial diagnosis of CPP, GnRH-stimulated LH peak, GnRH-stimulated FSH peak, Basal LH, FSH, oestradiol levels and uterine length for girls, testosterone levels and testicular volume for boys).

Listings will also be provided for all the summaries listed above separately in main study phase and extension phase.

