#### 5.7.1.1 Significance Testing and Estimations

The statistical analysis of efficacy is only descriptive therefore no formal statistical significance testing will be performed.

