**Table 1 Secondary Efficacy Endpoints and Evaluations**

Measure	Timepoint	Variable	Endpoint
Basal LH and FSH	Baseline, Month 3 and Month 6 (EOS)	LH and FSH concentration	Change in basal serum LH and FSH levels at Month 3 and Month 6 compared to baseline
Peak LH after GnRH	Baseline, Month 3 and	Peak LH levels after	Change in peak LH levels after GnRH stimulation test at

stimulation test	Month 6 (EOS)	GnRH stimulation (30, 60 and 90 minutes)	Month 3 and Month 6 compared to baseline; Proportion of children with LH suppression defined as stimulated peak LH $\leq 3$ IU/L after GnRH stimulation at Month 6.
Peak FSH levels after GnRH stimulation test	Baseline, Month 3 and Month 6 (EOS)	Peak FSH levels after GnRH stimulation (30, 60 and 90 minutes)	Change in peak FSH levels after GnRH stimulation test at Month 3 and Month 6 compared to baseline.
E2 and testosterone serum concentrations	Baseline, Month 3 and Month 6 (EOS)	Sex steroids levels	Proportion of children with sex steroids suppressed within prepubertal ranges (E2 $\leq 20$ pg/mL in girls and testosterone $\leq 0.3$ ng/mL in boys); Change in sex steroids levels compared to baseline
Pubertal stage (Tanner Method)	Baseline, Month 6 (EOS)	Pubertal stage	Change in pubertal stage (genital stage in boys, breast stage in girls and pubic hair stage in both sexes) compared to baseline; Proportion of children with stabilised pubertal stage compared to baseline
Auxological parameters (height, growth velocity, weight, BMI)	Baseline, Month 3 and Month 6 (EOS)	-	Change in auxological parameters compared to baseline
BA	Baseline, Month 6 (EOS)	-	Change in BA, difference between BA and CA compared to baseline
Uterine/ovary or testis volume	Baseline, Month 6 (EOS)	Gonad development	Change in uterine length in girls and testicular volume in boys compared to baseline

BA = Bone age; BMI = Body mass index; CA = Chronological age; E2 = Oestradiol; EOS = End of Study; FSH = Follicle-stimulating hormone; GnRH = Gonadotropin-releasing hormone; LH = Luteinising hormone.

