### 5.7.3.2 *Secondary Analysis*

For secondary efficacy endpoints related to a change at Month 3, 6 compared to baseline, the descriptive summary statistics (number of participants (n), mean, SD, median, quartiles, minimum, maximum) will be calculated on the mITT.

Exact two-sided 90% CI will also be constructed for all secondary endpoints expressed as proportions.

GV cm/y, Height, Weight, BMI, FSH, LH values, Bone age, difference between Chronological age and Bone age, mean Oestradiol/Testosterone, Uterine Length and Testicular Volume over time will be graphically presented via individual observed values (scatter) as well as mean and standard deviation of the observed values (Baseline, Month 3, and Month 6).

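### SAP 7 cuts chronological age to whole years while bone age stays fractional, so bone age minus chronological age is overstated by up to a year and its Month 6 change carries avoidable error

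*SAP*

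**What the plan says.** SAP section 7 has two age entries. Demographic age is taken at the consent date. Chronological age is computed afresh at each visit as (visit date - birth date + 1)/365.25, with the instruction "Chronological Age (years) will be calculated as follows and truncated to the largest integer that is less than or equal to the calculated result".

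Bone age is finer. Protocol 7.4.5 states "Bone age determination (in years and months) will be performed by X-rays of the hand and wrist", and SAP 7 handles readings recorded with a plus or minus by the rule "update 9+ to 9.25 and 10- to 9.75 in the summary analysis".

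The difference between the two is used in several places:

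- SAP Table 1 (secondary endpoints, Month 6): "Change in BA, difference between BA and CA compared to baseline". SAP Table 2 has the Month 12 counterpart for the extension.
- SAP 5.4 (baseline characteristics): "bone age, chronological age, the difference between bone age and chronological age".
- SAP 5.7.3.2 (figures): "Bone age, difference between Chronological age and Bone age".

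Baseline for these measures is Screening; Protocol 7.2 says that "baseline values correspond to those obtained with measurements performed at the Screening visit". The SAP gives no explicit formula for BA minus CA and no untruncated CA. The protocol contains no truncation rule, and SAP 2.6 reports no change from the protocol's statistical section.

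**The concern.** Subtracting a whole-year age from a fractional bone age leaves the discarded part of the child's age inside the difference. That part is never negative, so the level of BA minus CA is always pushed up.

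The change is affected differently. About half a year passes between Screening and Month 6, but a truncated age can move only by 0 (no birthday in the interval) or 1 (a birthday in it). Whether a child's difference appears to widen or narrow then depends partly on the birth date.

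At stake are a component of a secondary endpoint, a baseline table and a figure. Protocol 4.1 also requires a BA minus CA difference above one year at entry. A child whose true difference is 0.6 year could be tabulated at anything up to just under 1.6, so the baseline table could not be used to check that criterion.

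**Working it through.** **Inputs**

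- CA rule and formula: SAP 7.
- BA in years and months, or quarter-years: Protocol 7.4.5 and SAP 7.
- Screening Day -28 to Day -1; Month 6 at Day 182 ± 3 days: Protocol Table 1. Month 12 at Day 365 ± 3 days: Protocol Table 2.
- Sample size 28 evaluable, 32 enrolled: Protocol 11.2. The plan states no figure for error in BA minus CA, so these numbers only scale the result. They reproduce: with n = 28 and at least 24 responders, alpha is 0.0474 and power 0.858; 28/0.9 = 31.1, rounded up to 32.
- Assumptions, not in the documents: birthdays evenly spread relative to Screening; a range for the SD of the true change; truncation error independent of the true change.

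**Level.** Error in BA minus CA = CA - floor(CA), which lies from 0 to just under 1 year. With evenly spread birthdays the mean is 0.50 and the SD 0.29. This applies at Screening, Month 6 and Month 12, the visits where BA is read.

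**Month 6 change.** The shortest interval is Day -1 to Day 179, 179 days (0.490 year). The longest is Day -28 to Day 185, 212 days (0.580 year). Error in the change of BA minus CA = true CA advance - derived CA advance, so it runs from 0.49 - 1 = -0.51 to 0.58 - 0 = +0.58.

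For an interval of g years and evenly spread birthdays, the derived advance is 1 with probability g and 0 otherwise. The error then has mean 0 and SD √(g(1 - g)), which is 0.494 to 0.500 for every g in the window. A simulation of 4,000,000 children (age at Day 1 uniform from 6 to 9 years, screening 1 to 28 days earlier, visits within ± 3 days) gives a derived advance of 0 in 46.5% and 1 in 53.5%, with error SD 0.498.

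**Two illustrative children with the same BA readings (9.0, then 9.25)**

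| CA at Screening, Month 6 | True BA - CA | True change | BA - CA by SAP rule | Change by SAP rule |
|---|---|---|---|---|
| 7.95, 8.48 | 1.05, 0.77 | -0.28 | 2.00, 1.25 | -0.75 |
| 7.10, 7.63 | 1.90, 1.62 | -0.28 | 2.00, 2.25 | +0.25 |

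The true changes are equal; the derived ones differ by a full year and in sign.

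**Spread.** Observed SD = √(true SD² + 0.498²), and the truncation share of the variance is 0.498² divided by the square of that.

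| Assumed true SD (years) | Observed SD | Truncation share |
|---|---|---|
| 0.2 | 0.54 | 86% |
| 0.4 | 0.64 | 61% |
| 0.5 | 0.71 | 50% |
| 0.6 | 0.78 | 41% |
| 0.8 | 0.94 | 28% |

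**Trial mean.** Added standard error is 0.498/√32 = 0.088 year, or 0.498/√28 = 0.094. Multiplied by 1.96, that is about ±0.17 to ±0.18 year.

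**Uneven ages (illustrations, age at Day 1).** Bias in the mean Month 6 change of BA minus CA is +0.15 year for ages spread over 7.0 to 8.5, and -0.15 for 7.5 to 9.0. In the extremes it is +0.46 if all ages lie in 8.0 to 8.5 and -0.46 if all lie in 8.5 to 9.0. In those extremes the per-child SD drops to about 0.26 and 0.08, because noise has turned into bias.

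**Month 12 change.** The interval is close to a year. The derived advance is 1 in 96.4% and 2 in 3.6%, and the error SD falls to 0.19 year. The overstated level remains.

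**The case against.** The strongest point is that the SAP never writes out BA minus CA. It defines CA as a variable and lists the difference separately; the table shells are a separate document and the SAS code appendix is blacked out, so a programmer might in practice use exact age. That is possible, but the SAP supplies only the truncated CA, and a derivation recalculated at each visit has little other purpose than comparison with bone age. If exact age was intended, the text needs the same correction.

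Second, the SD of 0.50 depends on evenly spread birthdays, and the documents give no age distribution beyond the upper limits (under 9 for girls, under 10 for boys). This stands as a condition. When it fails, the error shifts from noise to bias. The half-year clusters are extremes and should not be read as expectations.

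Third, the documents give no SD for the true change, so the share of variance due to truncation can be shown only as a range. This also stands.

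Fourth, some bone ages appear to be recorded as a whole year with a plus or minus, so BA carries reading error that exact CA would not remove. True, but that does not justify adding a second, avoidable error.

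Fifth, the consequence is limited. SAP 5.7.1.1 states: "The statistical analysis of efficacy is only descriptive". Confidence intervals are planned only for proportions, and the mean change is unbiased if birthdays are even. This limits the severity. It does not remove the point, because in a descriptive analysis the means, SDs and plots are the result.

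**Conclusion.** The rule is wrong as written for BA minus CA and should be fixed. That the level is overstated by 0 to just under 1 year follows from the rule alone, once the truncated CA is used in the difference, which is the only reading the SAP supports. The mean overstatement of 0.50 year and the Month 6 error SD of about 0.50 year also need evenly spread birthdays. Without that, the mean Month 6 change is biased, by about 0.15 year in either direction in the moderate illustrations.

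The damage is confined to one component of a descriptive secondary endpoint, its extension counterpart, a baseline table and a figure. The primary endpoint, the sample size and the change in BA alone do not depend on CA.

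**What to change.** In SAP 7, derive chronological age as (visit date - birth date + 1)/365.25 without truncation, keeping at least two decimals. State that the difference is BA minus CA, with BA in decimal years and this untruncated CA, in every calculation, table, listing and figure. Keep whole-year truncation for demographic age only.

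With unrounded CA the truncation error is zero in both level and change. At two decimals the rounding error in the change has an SD of about 0.004 year, against about 0.50 now.

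The cost is one line of SAP text and one line of code. No new data are needed, because both dates are already in the formula.
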